2.3.4 Pharmacokinetic Endpoints

The PK endpoint is plasma obicetrapib concentrations in combination with ezetimibe and as monotherapy at Days 28, 84 and 112. PK samples will be collected with fasting laboratory samples (pre-dose on Days 28 and 84 and >24 hours after last dose of study drug).

2.3.5 Safety Endpoints

The safety and tolerability profiles of the obicetrapib 10 mg + ezetimibe 10 mg combination treatment group, obicetrapib 10 mg monotherapy treatment group, and the placebo group will be assessed by clinical laboratory values and the incidence of AEs.

3 STATISTICAL METHODOLOGY

3.1 General Considerations

3.1.1 Analysis Day

Analysis day will be calculated from the date of first dose of study drug. The day of the first dose of study drug will be Day 1, and the day immediately before Day 1 will be Day -1. There will be no Day 0.

3.1.2 Analysis Visits

Scheduled visits will be assigned to analysis visits as recorded on the Case Report Form (CRF). Early termination (ET) visits will be assigned to analysis visits according to the following visit windows:

Analysis Visit	Target Analysis Day	Low Analysis Day	High Analysis Day
Day 1	1	NA	NA
Day 28	28	2	56
Day 84 (EOT)	84	57	98
Day 112 (Safety FUP)	112	99	

Unscheduled visits record on the CRF will not be re-assigned and will remain labelled as unscheduled.

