Clinically significant abnormal laboratory or other examination findings (eg, ECG) that are detected during the study or are present at the date of the first dose of study treatment and significantly worsen during the study should be reported as AEs, as described below. The Investigator will exercise his or her medical and scientific judgment in deciding whether an abnormal laboratory finding or other abnormal assessment is clinically significant. Clinically significant abnormal laboratory values occurring during the study will be followed until repeat tests return to normal, stabilize, or are no longer clinically significant. Abnormal test results that are determined to be an error should not be reported as an AE. Laboratory abnormalities or other abnormal clinical findings (eg, ECG abnormalities) should be reported as an AE if any of the following are applicable:

- If an intervention is required as a result of the abnormality;
- If action taken with the study drug is required as a result of the abnormality; or
- Based on the clinical judgment of the Investigator.

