3.1.3 Definition of Baseline

Unless otherwise stated, baseline is defined as the last measurement prior to the first dose of study drug.

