3.4.1 Primary Efficacy Endpoints

Primary Analysis

The primary efficacy endpoint is the percent change from Day 1 to Day 84 in LDL-C (as determined by approach 1 above) for the combination treatment group compared to the placebo group. The percent change will be calculated from Day 1 (Baseline) to each measurement taken at Day 28 and Day 84.

The percent change in LDL-C from Day 1 to Day 84 for each treatment group is defined mathematically as μ_j , where j stands for the j^{th} treatment ($j=0,1,2$) and the subscript 0 refers to the placebo group. The hypotheses testing to the percent change in LDL-C from Day 1 to Day 84 is then defined statistically as following:

$$H_0: \mu_j - \mu_0 = 0, H_1: \mu_j - \mu_0 \neq 0, \text{ where } j=1,2$$

LDL-C values will be summarized by visit and treatment group; visit values, change from baseline and percent change from baseline will be summarized. Missing data patterns in the LDL-C values will also be summarized by treatment group.

The analysis of the percent change from Day 1 to Day 84 in LDL-C will be performed using a mixed model for repeated measures (MMRM) approach. The analysis will include fixed effects for treatment, visit, and treatment-by-visit interaction, along with a covariate of the baseline value as a continuous covariate. Randomization was stratified according to Screening Visit LDL-C value (≥ 100 or < 100 mg/dL) to ensure a similar distribution of LDL-C values across all treatment groups. However, the MMRM model will include the original scale of the baseline LDL-C values as continuous covariate.

The Restricted Maximum Likelihood estimation approach (REML) will be used with an unstructured covariance matrix. The least-squares means (LSMean), standard errors, and 2-sided 95% confidence intervals for the combination treatment group and for the comparison of the combination treatment group to the placebo group will be provided.

The MMRM approach will include all available assessments of percent change in LDL-C from Day 1 to Day 28 and Day 84. The model assumes that the data are missing at random (MAR). If any data are missing, the model will use all information from the other time points to estimate the mean treatment difference at the given time point. No imputation of missing data will be performed for the primary analysis.

The primary analysis will be conducted for the mITT, ITT, and PP Populations.

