3.6.1 Adverse Events (AEs)

AEs will be categorized by primary system organ class and preferred term as coded using the MedDRA (version 24.1) category designations.

An overview of treatment-emergent AEs (TEAEs) will be provided including counts and percentages of participants (and event counts) with the following:

- Any TEAEs overall and by maximum severity
- Any study drug related TEAEs, overall and by maximum severity
- Any TEAEs leading to discontinuation of study drug
- Any treatment-emergent serious AEs (TESAEs)
- Any study drug related TESAEs
- Any TEAEs leading to death

The TEAEs described above will be summarized separately by System Organ Class and Preferred Term.

Listings will be presented specifically for TEAEs, TESAEs and TEAEs leading to discontinuation of study drug.

3.6.2 *Clinical Laboratory Tests*

Blood for chemistry and hematology will be obtained as indicated in Table 1 Schedule of Procedures and sent to a central laboratory for analysis. See Appendix A for a complete list of analytes. Blood samples for chemistry and hematology must be obtained under fasting conditions (i.e., after the participant has fasted for ≥ 10 hours).

Laboratory values will be summarized descriptively, including the change and percent change from baseline. In addition, shift tables will be presented to describe the change in laboratory parameter values at post-baseline visits using normal range categories (low, normal, and high).

All safety laboratory data will be presented in participants listings.

3.6.3 *Vital Signs*

Vital signs including body temperature, heart rate, and triplicate blood pressure will be measured at all scheduled visits. Triplicate blood pressure measurements will be averaged for analysis.

Values and changes from baseline will be summarized with descriptive statistics at each visit.

Separate plots will be provided for the change from baseline in systolic and diastolic blood pressure by visit.

Height and weight will be measured at the Screening Visit only. Body Mass Index (BMI) will be derived as weight/(height/100)² (kg/m²); rounded and displayed to 1 decimal place.

3.6.4 *Electrocardiograms*

A single, standard 12-lead ECG will be performed on-site at the Screening Visit and read locally.

ECG data will be summarized with descriptive statistics and presented in participant listings.

3.6.5 *Physical Examinations*

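### On the natural reading of the SAP, a laboratory abnormality found only at an unscheduled test is missing from the by-arm shift tables, and no worst post-baseline category captures it

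*SAP*

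**What the plan says.** SAP 3.1.2 sorts results into analysis visits by three rules. Scheduled visits keep the visit label on the CRF, with no day limit. For the second group, "Early termination (ET) visits will be assigned to analysis visits according to the following visit windows": Days 2 to 56 become Day 28, Days 57 to 98 become Day 84, and Day 99 onward becomes Day 112. For the third group, "Unscheduled visits record on the CRF will not be re-assigned and will remain labelled as unscheduled".

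On laboratory safety, SAP 3.6.2 says that "shift tables will be presented to describe the change in laboratory parameter values at post-baseline visits using normal range categories" of low, normal and high. No worst post-baseline category is planned. All safety laboratory data are to be listed. Protocol 8.1 foresees tests outside the schedule: "Clinically significant abnormal laboratory values occurring during the study will be followed until repeat tests return to normal", or until they stabilize or cease to be clinically significant.

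On efficacy, SAP 3.4 ties the LDL-C source for the primary endpoint (its approach 1) to scheduled visits. SAP 3.4.1 adds: "The MMRM approach will include all available assessments of percent change in LDL-C from Day 1 to Day 28 and Day 84". It also says: "No imputation of missing data will be performed for the primary analysis". Protocol 7.1 asks sites to reschedule a visit when the participant has not fasted. Neither document says how a repeat of a lost or invalid sample is labelled.

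**The concern.** Clinical laboratory values are one of the two safety assessments named in SAP 2.3.5, the other being adverse events. The shift table is where they are compared between arms by normal-range category. A participant who is normal at every scheduled visit but abnormal at a symptom-driven test would be shown there as normal throughout, although the abnormal value is in the database. Listings hold the value but give no comparison by arm.

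A smaller question arises for LDL-C. An early-termination sample from as early as Day 57, which is 84 − 57 = 27 days before target, counts as Day 84. A repeat of a failed Visit 4 sample taken a few days after target does not, if the CRF records it as unscheduled. An observed outcome would then be handled as missing.

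**Working it through.** **The plan's own figures.** Inputs from Protocol 9.2.5 and SAP 2.2.2: difference 30 points, SD 15, 36 evaluable per group, 1-sided 0.025, dropout about 5%.
- SE of the difference = 15 × √(2/36) = 3.54.
- 30 / 3.54 = 8.49, far above 1.96. Power is above 99.99%, so the stated power of more than 90% is met.
- 108 / 0.95 = 113.7, giving 114; 36 / 0.95 = 37.9, giving 38 per group. Both agree with the documents.

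**The laboratory gap.** Inputs from Protocol Appendix A: on treatment after baseline, scheduled chemistry and hematology fall at Day 28 (±2) and Day 84 (±2).
- Visit 3 window: Days 26 to 30. Visit 4 window: Days 82 to 86.
- Days clear of both and between them: 31 to 81, which is 81 − 31 + 1 = 51 days.
- 51 / 84 = 61% of the treatment days.

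**Where a post-baseline laboratory result goes under SAP 3.1.2 and 3.6.2.**
- Scheduled: the labelled analysis visit, hence the shift table.
- Early termination on Days 31 to 56: Day 28. On Days 57 to 81: Day 84. Both reach the shift table.
- Unscheduled: no analysis visit. Shift tables built by visit then have no row for it, and no worst-value category collects it. It reaches the listings. It reaches the adverse event tables only if it meets a Protocol 8.1 condition: an intervention, action taken with study drug, or the investigator's judgment.

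**What follows if a Day 84 lipid repeat is labelled unscheduled.**
- The primary MMRM treats Day 84 as missing but keeps any Day 28 value.
- Sensitivity analysis 1 imputes Day 84 from a model fitted to placebo observations.
- Sensitivity analysis 2, the Day 84 ANCOVA on the same LDL-C source, has no outcome for that participant.
- The participant has no assigned Day 84 value for the Per-Protocol Population (SAP 3.2.3) or the responder analysis (SAP 3.4.3).

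**Size of that loss.** The calculation ignores Day 28 data, so it is a worst case.
- One value lost in one arm: 15 × √(1/35 + 1/36) = 3.56, against 3.54, a rise of under 1%.
- The documents give no rate of failed samples. Assuming 34, 30 or 20 Day 84 values per group, 15 × √(2/n) gives an SE of 3.64, 3.87 or 4.74. Power stays above 99.99% in each case.

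**The case against.** The strongest reply is that SAP 3.6.2 excludes nothing by name. It refers to post-baseline visits, not to scheduled or analysis visits, and SAP 6 leaves programming detail to a separate document that is not available here. The sponsor may therefore intend unscheduled results to count. Clinically significant abnormalities also reach the adverse event tables, a symptom that prompted a test would itself be an adverse event, and safety is descriptive only.

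Part of this stands: exclusion from the shift tables is the natural reading, not an express rule. But SAP 3.1.2 does state a rule for unscheduled results, and nothing in SAP 3.6.2 brings them back. Adverse event reporting depends partly on judgment and does not replace a by-arm display of laboratory categories.

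Four stronger readings are tempting, and the documents do not support them.
- A reader might infer that every abnormality found between Day 28 and Day 84 escapes the tables. Early-termination results in that span are assigned to a visit. Counting Days 29 to 83 (55 days, 65%) also overlooks the ±2-day windows, which allow scheduled tests on Days 29, 30, 82 and 83.
- A reader might infer that unscheduled results can serve no analysis visit at all. SAP 3.1.3 says that "baseline is defined as the last measurement prior to the first dose of study drug", so an unscheduled pre-dose result can be the baseline.
- A reader might infer that a repeat Day 84 lipid sample is always lost. Scheduled visits follow the CRF label, so a rescheduled visit entered as Visit 4 is Day 84.
- A reader might infer that power is threatened. On the plan's own inputs it is not.

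**Conclusion.** The point holds for unscheduled post-baseline results. As written, the plan leaves a laboratory abnormality found only at such a test out of the by-arm shift tables, and 51 of the 84 treatment days (61%) lie between the two on-treatment visit windows. This rests on taking the visits in SAP 3.6.2 to be the analysis visits of SAP 3.1.2. How many participants it would affect cannot be judged, because the documents do not give the number of unscheduled samples.

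The lipid part is secondary. It depends on a repeat being labelled unscheduled, and its effect on precision is negligible. The reason to settle it is that an observed Day 84 value should not be set aside, or accepted after the fact, without a rule written beforehand.

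**What to change.** **Main change, SAP 3.6.2.** Add a worst post-baseline category to the laboratory shift tables, derived from scheduled, early-termination and unscheduled results. Keep the by-visit tables as they are.

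**Secondary change, SAP 3.1.2.** State that when the scheduled Day 28 or Day 84 lipid result is missing or invalid, a fasting repeat recorded as unscheduled is analysed as that visit if it falls within a pre-specified limit. The limit should lie inside the SAP's own analysis window (Days 2 to 56 or Days 57 to 98). The documents supply no figure for it, so the sponsor should choose and justify one. Flag repeats taken after the last dose and show the result without them.

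**Cost.** SAP wording and a small amount of extra programming, using data already collected, with no change to study conduct. Dosing ends on Day 84, so a few repeat values may be off drug by some days; the flag and the second result address that. Both changes should be in place before unblinding.

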3.1.3 Definition of Baseline

Unless otherwise stated, baseline is defined as the last measurement prior to the first dose of study drug.

3.1.4 Summary Statistics

Categorical data will generally be summarized with counts and percentages of participants. The denominator used for the percentage calculation will be clearly defined. Continuous data will generally be summarized with descriptive statistics including n (number of non-missing values), mean, median, standard deviation, minimum, and maximum.

3.1.5 Evaluation of Site Effect

This is a multi-centre study. Sites will not be pooled for any planned inferential analysis but may be pooled for subgroup analysis to assess the heterogeneity of treatment effects among pooled sites. The final pooling algorithm, if needed, will be specified before treatment unblinding, and will

be provided as an addendum to the SAP. Additionally, a review of by-site effects will be performed in the context of data listing review.

3.1.6 *Handling of Dropouts and Missing Data*

Date Values

In cases of incomplete dates (e.g., AE, concomitant medication, and medical history start and/or stop dates), the missing component(s) will be assumed as the most conservative value possible. For example, if the start date is incomplete, the first day of the month will be imputed for the missing day and January will be imputed for the missing month. If a stop date is incomplete, the last day of the month will be imputed for the missing day and December will be imputed for the missing month. Incomplete start and stop dates will be listed as collected without imputation.

Date imputation will only be used for computational purposes such as treatment-emergent status. Actual date values, as they appear in the original CRFs, will be presented within the data listings.

Non-Date Values

For sensitivity analyses of the primary efficacy endpoint, missing values will be imputed using multiple imputation methods (see Section 3.4.1). For the analyses of secondary and exploratory efficacy endpoints, no imputation will be made for missing values. Safety data will be used according to availability, with no imputation for missing data.

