#### **8.1** Adverse Events

An AE is defined as any untoward medical occurrence in a clinical investigation participant administered a pharmaceutical product, which does not necessarily have a causal relationship with this treatment. An AE can therefore be any unfavorable and/or unintended sign (including an abnormal laboratory finding), symptom, or disease temporally associated with the use of an investigational medicinal product, whether or not related to the investigational medicinal product. All AEs, including observed or volunteered problems, complaints, or symptoms, are to be recorded on the appropriate eCRF.

AEs, which include clinical laboratory assessment variables, will be monitored and documented from the time of first dose of study treatment until completion of Visit 5. Participants should be instructed to report any AE that they experience to the Investigator, whether or not they think the event is due to study drug. Beginning at the date of the first dose of study treatment, Investigators should make an assessment for AEs at each visit and record the event on the appropriate AE eCRF.

Wherever possible, a specific disease or syndrome rather than individual associated signs and symptoms should be identified by the Investigator and recorded on the eCRF. However, if an observed or reported sign or symptom is not considered a component of a specific disease or syndrome by the Investigator, it should be recorded as a separate AE on the eCRF. Additionally, the condition that led to a medical or surgical procedure (eg, surgery, endoscopy, tooth extraction, or transfusion) should be recorded as an AE, not the procedure itself.

Any medical condition already present at the date of the first dose of study treatment should be recorded as medical history and not be reported as an AE unless the medical condition or signs or symptoms present at baseline changes in severity, frequency, or seriousness at any time during the study. In this case, it should be reported as an AE.

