## 10.1.5 Data Validation

Validation checks programmed within the EDC system, as well as supplemental validation performed via review of the downloaded data, will be applied to the data in order to ensure accurate, consistent, and reliable data. Data identified as erroneous, or data that are missing, will be referred to the site for resolution through data queries.

The eCRFs must be reviewed and electronically signed by the Investigator.

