3.6 Safety Assessment

The Safety Population will be the primary population for the safety analyses. All safety endpoints will be summarized descriptively by treatment group and overall. No statistical inference will be applied to the safety endpoints.

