6 PROGRAMMING SPECIFICATIONS

Analyses will be performed using SAS® version 9.4 or higher. All available data will be presented in subject data listings which will be sorted by subject and visit date as applicable. Detailed Programming Specifications will be provided in a separate document.

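### Partial adverse event start dates have no floor at first dose and TEAE is undefined, so some on-treatment events can be classed as pre-treatment

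*SAP*

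**What the plan says.** SAP 3.1.6 (Handling of Dropouts and Missing Data, Date Values) covers incomplete dates for adverse events, concomitant medications and medical history together. Its principle is that "the missing component(s) will be assumed as the most conservative value possible". Its example for start dates is that "if the start date is incomplete, the first day of the month will be imputed for the missing day and January will be imputed" for a missing month; stop dates go to the end of the month or to December. On use, it says: "Date imputation will only be used for computational purposes such as treatment-emergent status". It has no separate rule for a partial start date that falls in the month or year of first dose.

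SAP 3.6.1 builds its adverse event overview and its tables by system organ class and preferred term on TEAEs and treatment-emergent serious adverse events (TESAEs). It adds: "Listings will be presented specifically for TEAEs, TESAEs and TEAEs leading to discontinuation of study drug". It gives no start point, end point or worsening rule for the term. The SAP abbreviation list only spells the term out, and the protocol does not define it.

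Protocol 8.1 says that adverse events "will be monitored and documented from the time of first dose of study treatment until completion of Visit 5". A condition already present at first dose is medical history unless it later changes in severity, frequency or seriousness.

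**The concern.** Moving a partial start date to the earliest possible day is cautious for some purposes, but not for deciding whether an adverse event began on treatment. Here it can only push the start backwards, possibly past first dose. Because the protocol collects adverse events only from first dose, an event on the adverse event form is by design an on-study event. Dating it before first dose is therefore the less cautious choice, and the SAP's example works against its own principle.

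An affected event would drop out of the TEAE and TESAE summaries and out of the listings named in SAP 3.6.1. Where only the day is missing, the loss falls entirely in the calendar month of first dose, that is, in early exposure. Safety and tolerability, assessed partly by adverse event incidence, is a stated objective. With 38 participants per group, one participant wrongly left out shifts an incidence by 1/38 = 2.6 percentage points.

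**Working it through.** The plan states no figure on this point, so there is none to reproduce. The check applies the SAP 3.1.6 example literally and asks when the imputed start falls before first dose.

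**Inputs**
- Day missing: start set to the 1st of the recorded month. Day and month missing: start set to 1 January of the recorded year (SAP 3.1.6).
- Adverse events are collected from first dose to Visit 5, nominally Days 1 to 112 (Protocol 8.1 and Appendix A).
- Assumptions: TEAE means onset on or after first dose; first doses are spread evenly over a 365-day year; onset is uniform over Days 1 to 112.
- Pairs enumerated: 365 × 112 = 40,880. The years 2021, 2022 and 2023 give the same result.

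**Example, first dose 15 March**

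| Onset | Recorded as | Imputed by the rule | Before first dose? | Imputed with floor |
|---|---|---|---|---|
| 20 March | March | 1 March | Yes | 15 March |
| 10 April | April | 1 April | No | 1 April |
| 10 May | year only | 1 January | Yes | 15 March |

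**Day missing.** With first dose on day d of a month of L days, and d > 1, every onset from day d to day L is misclassified. The share is (L − d + 1)/112; for d = 1 it is 0.
- d = 2: 27/112 = 24.1% (L = 28) to 30/112 = 26.8% (L = 31)
- d = 15: 14/112 = 12.5% (L = 28) to 17/112 = 15.2% (L = 31)
- d = 31: 1/112 = 0.9%

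Summed over a month this is L(L − 1)/2 pairs. Over the year: 7 × 465 + 4 × 435 + 378 = 5,373 pairs, and 5,373/40,880 = 13.1%. Among day-missing events with onset in the calendar month of first dose, the share is 5,373/5,738 = 93.6%, that is, every case unless first dose falls on the 1st. Day-missing events in a later month are unaffected.

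**Day and month missing.** With first dose on day k of the year, and k > 1, the misclassified onsets are those in the same calendar year: min(112, 366 − k).
- k = 2 to 254: 253 × 112 = 28,336
- k = 255 to 365: 111 + 110 + … + 1 = 6,216
- Total 34,552, and 34,552/40,880 = 84.5%. By first-dose date the range is 0 to 100%.
- First dose January to June: 180/181 = 99.4%. July to December: (73 × 112 + 6,216)/(184 × 112) = 14,392/20,608 = 69.8%.

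**Share of all adverse events.** The documents do not say how often dates will be partial. Taking 1 to 10% of events with only the day missing as an assumed range: 0.01 × 0.131 = 0.13%, and 0.10 × 0.131 = 1.3%.

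**With a floor.** Taking the later of the rule's date and the first-dose date, 0 of 40,880 pairs are misclassified under either pattern. This follows by construction, because every onset enumerated is on or after first dose.

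**The case against.** The best defence is that the documents allow a reading under which nothing is lost. Adverse events are collected only from first dose, and Protocol 9.2.3 promises summaries of adverse events with no treatment-emergent filter. SAP 5 lists the changes from the protocol and mentions no narrowing of those summaries. TEAE could then simply mean every event on the form. The 1st-of-month wording is also only an example, and the governing principle of caution would keep a doubtful event in. A first-dose floor may also sit in the separate programming specifications that SAP 6 mentions, which were not available here.

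These readings are possible, but none is stated. The first conflicts with the SAP's statement that imputed dates serve to decide treatment-emergent status. The second sets the principle against the only worked rule given for start dates, and a programmer cannot follow both. On the third, a rule that decides which events are counted belongs in the SAP.

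Other parts of the defence do stand:
- SAP 6 says "All available data will be presented in subject data listings", and SAP 3.1.6 shows dates there as collected, so an affected event should remain visible in the general listings.
- Under Protocol 10.1.5, "data that are missing, will be referred to the site for resolution through data queries", which should make partial dates uncommon. Losing both day and month is especially unlikely in a 16-week study with scheduled visits, so the 84.5% applies to a rare case.
- Serious events are reported within 24 hours with follow-up (Protocol 8.3), so an unresolved onset date is less likely for them.
- Safety carries no inference: "All safety endpoints will be summarized descriptively by treatment group and overall". The rule is the same in all groups.

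**Conclusion.** The concern holds, as a minor point. As written, SAP 3.1.6 can date an on-treatment adverse event before first dose, and no TEAE definition prevents that event from leaving the tables. The direction of the error does not depend on the uniform-date assumptions; the percentages do. Under those assumptions and an onset-based TEAE, 13.1% of day-missing events are misclassified (range 0 to 26.8%), and 84.5% of events missing day and month. Events with complete dates are unaffected.

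Confidence is high that the rule has no floor and that TEAE is undefined. It is low on how many events are affected, because the documents give no frequency of partial dates. No test, error rate or efficacy result is touched. Concomitant medication status is not affected in the same way, since under SAP 3.3.6 a medication counts as prior only if it stopped before first dose, and partial stop dates are imputed late.

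**What to change.** Before database lock, amend the SAP as follows:

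1. In 3.6.1, define a TEAE as an adverse event with onset or worsening on or after the first dose of study drug. State an end point too; the collection period in Protocol 8.1 ends at Visit 5. For a pre-existing condition reported because it worsened, say that the start date is the date of worsening.
2. In 3.1.6, for adverse events only: if the known parts of the start date are compatible with onset on or after first dose, and any stop date is not before first dose, impute the later of the existing rule's date and the first-dose date. Say also what happens when the start date is missing altogether, which the present text does not cover.
3. Otherwise keep the existing rule, including for medical history and concomitant medications.

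The core change is two SAP sentences and one line of derivation code; the end point, the worsening date and the wholly missing date need a few words more. TEAE counts may rise slightly. If the programming specifications already contain a floor, the cost is only to state it in the SAP.
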